1.3 DETERMINATION OF SAMPLE SIZE

The sample size of the study is determined based on power calculations for the primary endpoint of annualized rate of acute moderate or severe COPD exacerbations over the 52-week treatment period. Assuming the number of exacerbations follows a negative binomial distribution with a dispersion parameter of 1, a placebo annualized rate of exacerbations of 1.5, an average treatment duration of 0.95 year (to account for an average of 5% of the planned treatment period with missing data), and a randomization ratio of 1:1 to the two treatment arms, with 924 randomized patients (462 for each treatment arm), the study will have 90% power to detect a 25% relative risk reduction (ie, annualized rate of 1.125 for the dupilumab group) in the annualized rate of moderate or severe COPD exacerbations at the 2-tailed significance level of $\alpha=0.05$. With the addition of an interim analysis, the final alpha may be reduced to 0.049, which maintains approximately 90% power (see [Section 3](#) for further details).

Patients will be randomized using a 1:1 randomization ratio to dupilumab 300 mg q2w or placebo. Randomization will be stratified by country, ICS dose (high dose ICS [yes/no]) at baseline, and smoking status at screening (current smokers or not).

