If patients withdraw from the study before Visit 16 (Week 52), moderate or severe exacerbation events that may occur after study discontinuation will not be observed. These patients are considered as patients with missing data on moderate or severe exacerbation. Number of patients with missing data, reasons and timing for patient withdrawals will be summarized by treatment groups. Summary statistics of selected demographic and baseline disease characteristics will be provided for patients with missing data and patients with complete data separately. In addition, the following sensitivity analyses will be conducted to assess the robustness of the conclusion based on the primary analysis.

Pattern mixture model - multiple imputation (PMM-MI)

For each patient with missing data of moderate or severe exacerbation events, individual bi-weekly event probability will be estimated using observed data with adjustment of the planned treatment group, region (pooled country), ICS dose at baseline (high dose ICS [yes/no]), smoking status at screening (current smokers or not), baseline disease severity (as % predicted post-bronchodilator FEV₁), and number of moderate or severe COPD exacerbation events within one year prior to the study (≤ 2 , 3, or ≥ 4). The total number of AECOPD moderate or severe events (on bi-weekly basis) will be calculated based on data imputed using multiple imputation.

Control-based PMM-MI

For each patient with missing data of moderate or severe exacerbation events, individual bi-weekly event probability will be estimated using observation in the placebo arms only, with adjustment of region (pooled country), ICS dose at baseline (high dose ICS [yes/no]), smoking status at screening (current smokers or not), baseline disease severity (as % predicted post-bronchodilator FEV₁), and number of moderate or severe COPD exacerbation events within one year prior to the study (≤ 2 , 3, or ≥ 4). The total number of AECOPD moderate or severe events (on bi-weekly basis) will be calculated based on data imputed using multiple imputation.

Tipping point analysis

For each patient with missing data of moderate or severe exacerbation events, the bi-weekly event will be imputed in a similar fashion as PMM-MI based on various odds values. If the patient is on dupilumab, the predicted odds will be increased; if the patient is on Placebo, the predicted odds value will be decreased. The adjusted rate will then be used to impute the number of events that

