2.4.4.3 Multiplicity issues

Multiplicity is considered for performing an interim analysis and for testing multiple endpoints. The overall Type-I error rate will be controlled at the two-sided 0.05 level.

An interim analysis will be performed using the Kim-DeMets (9) spending function when the information fraction is ≥ 0.92 based on follow-up time for the primary endpoint of annualized rate of moderate or severe COPD exacerbations over 52-week treatment period (see [Section 3](#)).

A hierarchical testing procedure will be used for testing primary, key secondary and other endpoints. If the primary endpoint does not demonstrate efficacy at this interim analysis then the study will remain blinded and the primary endpoint will be retested at the 52-week final analysis time point with an $\alpha=0.049$. If the primary endpoint demonstrates efficacy at this interim analysis based on the alpha allocated, then the rest of the multiplicity-controlled endpoints will be tested with $\alpha=0.05$. The comparisons will be tested based on the hierarchical order below.

1) Primary efficacy endpoints:

- Annualized rate of moderate or severe COPD exacerbations over the 52-week treatment period compared to placebo.

2) Secondary/exploratory efficacy endpoints:

- Change in pre-bronchodilator FEV₁ from baseline to Week 12 compared to placebo
- Change in pre-bronchodilator FEV₁ from baseline to Week 52 compared to placebo
- Change in pre-bronchodilator FEV₁ from baseline to Week 12 compared to placebo in the subgroup of patients with baseline FeNO ≥ 20 ppb
- Change in pre-bronchodilator FEV₁ from baseline to Week 52 compared to placebo in the subgroup of patients with baseline FeNO ≥ 20 ppb
- Change from baseline to Week 52 in SGRQ total score compared to placebo
- Proportion of patients with SGRQ improvement ≥ 4 points at Week 52 compared to placebo
- Change in E-RS COPD total score from baseline to Week 52 compared to placebo
- Annualized rate of moderate or severe COPD exacerbation compared to placebo over the 52-week treatment period in the subgroup of patients with baseline FeNO ≥ 20 ppb

The study is considered positive when the primary endpoint achieves statistical significance.

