Appendix K Handling of missing data

Annualized rate of moderate or severe exacerbation events during the 52-Week period

- ***Pattern mixture model - multiple imputation (PMM-MI)***

Step 1. The 52-week observation period is partitioned into bi-weekly (2-week) segments.

By clinical definition, a patient can have at maximum 1 moderate or severe exacerbation event per two weeks. For each patient, his/her event count over 52 weeks is broken down into a series of binary outcomes across each of the 26 bi-weekly segments (52 weeks). In the analysis, for each patient, in each bi-weekly segment, an imputation flag (imputefl) will indicate whether the patient needs imputation in that segment.

Step 2. Estimation for the bi-weekly binary event probability using observed data

Within each bi-weekly segment, the logistic regression model will be fitted to the observed data to model coefficient estimates and the estimated variance-covariance matrix, with adjusting for the planned treatment group, region (pooled country), ICS dose at baseline (high dose ICS [yes/no]), smoking status at screening (current smokers or not), baseline disease severity (as % predicted post-bronchodilator FEV₁), and number of moderate or severe COPD exacerbation events within one year prior to the study (≤ 2 , 3, or ≥ 4). From the posterior distribution of the model coefficients, we randomly draw 40 sets of iid samples. As a result, for each patient and in each bi-weekly segment, 40 estimated probabilities can be obtained by using the 40 samples of coefficients and the patient's covariate values.

Step 3. Multiple Imputation of binary event by bi-weekly segment after study withdrawal

If a patient withdraws from the study at the kth ($1 \leq k < 14$) day of Segment i prior to Week 52, and experienced a moderate or severe exacerbation within the first k days, this patient will be considered as “observed” (imputefl=0) up to Segment i and will need imputations (imputefl=1) from Segment i+1 to Segment 26 (Week 52).

If a patient withdraws from the study at the kth ($1 \leq k < 14$) day of Segment i prior to Week 52, and has no moderate nor severe exacerbation in Segment i, this patient will be considered as “observed” (imputefl=0) up to Segment i-1 and will need imputations (imputefl=1) from Segment i to Segment 26 (Week 52).

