For a patient who needs imputation from Segment i+1 to Segment 26, in each bi-weekly segment, 40 independent random samples will be respectively drawn from 40 estimated Bernoulli distributions, whose probabilities are obtained in Step 2.

For each patient who early withdraws from the study, 40 sets of complete event count data can be obtained by summing the observed event count prior to withdrawal and each series of imputed binary events after withdrawal up to Week 52.

Step 2 and 3 can be realized by using PROC MI in SAS. Sample code can be found below:

```
#  
surf#pl#gwd@gg#vhg@<;496;;#qlpsxwh@73#rxw@rxwgwdw>#  
e|#prqwk>#  
fodvv#rxwfrph#wuw34sq##fqw|ju4#lfv#frsgqxp>#  
prqrwrqh#uhj#+IHY4eo2ghwdlov,>#  
orj1vwlf#+rxwfrph@wuw34sq#fqw|ju4#lfv#vprnlqj#IHY4eo#  
frsgqxp2ghwdlov#GHVFHQGLQJ,>#  
ydu##fqw|ju4#lfv#vprnlqj#IHY4eo#wuw34sq#frsgqxp#rxwfrph>#  
uxq>#
```

Step 4. Combining MI results by Rubin's formula

A negative binomial model with the same set of covariates as in the primary analysis will be fitted with 40 sets of complete datasets obtained in Step 3, so as to obtain 40 sets of treatment effect estimates (in log-scale) and p-values accordingly. Log transformed observation duration will be the offset variable for patients who complete the 52-Week treatment/study period, and log transformed 52 weeks will be the offset variable for patients who discontinue the study before Visit 16 (Week 52). At last, the SAS MIANALYZE procedure will be used to generate statistical inferences by combining results (in log-scale) from the 40 analyses using Rubin's formula. These and their confidence interval limits are then exponentiated to derive relative rates. Of note, the rule will be applied on the log risks and log risk ratio.

Step 4 can be realized by using PROC MIANALYZE in SAS. Sample code can be found below

```
#  
surf#pldqdo|}h#gwd@uubfrqy>#  
e|#Odeho>#  
prghohiihf#Hvwlpdwh>#  
vwghuu#VwgHuu>#  
rgv#rxwsxw#SdudphwhuHvwlpdwhv@uubsrrohg>#  
uxq>#  
surf#pldqdo|}h#gwd@dhbfrqy>#  
e|#WUW34SQ>#  
prghohiihf#Hvwlpdwh>#  
vwghuu#VwgHuu>#  
rgv#rxwsxw#SdudphwhuHvwlpdwhv@dhubsrrohg>#  
uxq>#  
/* estimated RR and corresponding 95% CI */  
data pouttx;  
  
set uubsrrohg;  
if Parameter="txval";  
rr = exp(estimate);  
uxq>#
```

- ***Control-based PMM-MI***

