All steps are the same as the aforementioned approach except in Step 2: the individual bi-weekly mean probability will be calculated based on observations in matching placebo arms only, with adjustment of missing observation duration.

- ***Tipping point analysis***

The tipping point analysis for severe exacerbation events will use the similar approach as PMM-MI with tipping values for the odds.

Step 1. Estimation for the bi-weekly binary event probability using observed data

Within each bi-weekly segment up to Week 52, the logistic regression model will be fitted to the observed data to obtain the model coefficient estimates and the estimated variance covariance matrix, with adjusting for the planned treatment group, region (pooled country), ICS dose at baseline (high dose ICS [yes/no]), smoking status at screening (current smokers or not), baseline disease severity (as % predicted post-bronchodilator FEV₁), and number of moderate or severe COPD exacerbation events within one year prior to the study (≤ 2 , 3, or ≥ 4). From the posterior distribution for the model coefficients, we randomly draw 40 sets of iid samples. As a result, for each patient and in each segment, 40 estimated binary event probabilities can be obtained by using the 40 samples of coefficients and the patient's covariate values.

Step 2. Tip on the bi-weekly binary odds (the probability of having an event in the segment over the probability of being event-free in the segment)

Within each segment, for the patients from the placebo group and need imputation in that segment, the estimated odds for binary event will be deflated by decreasing a positive amount; for the patients from the treatment group and need imputation in that segment, the estimated odds for binary event will be inflated by increasing a positive amount. After the deflation/inflation, 40 sets of binary event probabilities can be obtained for the placebo and treatment groups, respectively.

Step 3. Multiple Imputation of binary event by bi-weekly segment after study withdrawal

For a patient who needs imputation from Segment i+1 to Segment 26, in each segment, 40 independent random samples will be respectively drawn from 40 estimated Bernoulli distributions, whose probabilities are obtained in Step 2.

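### The PMM-MI and tipping-point imputations of exacerbations ignore each patient's own on-study events, so their standard error is too small and the rate ratio is biased if withdrawal follows exacerbations

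*SAP*

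**What the plan says.** The primary analysis is a negative binomial regression on observed events, with follow-up time as offset and no imputation. SAP 2.4.4.1 adds three sensitivity analyses for patients who leave the study before Week 52, and Appendix K gives their steps.

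- **PMM-MI.** In 2.4.4.1, "individual bi-weekly event probability will be estimated using observed data with adjustment of the planned treatment group", plus region, ICS dose, smoking status, % predicted FEV1 and prior-year exacerbation category. Appendix K Step 2 makes this a separate fit per segment: "Within each bi-weekly segment, the logistic regression model will be fitted to the observed data to model coefficient estimates and the estimated variance-covariance matrix". In Step 3, for each missing segment, "40 independent random samples will be respectively drawn from 40 estimated Bernoulli distributions". Imputed events are added to the observed count, and withdrawn patients receive a full 52-week offset. The sample PROC MI code agrees: it is a BY-group run over time, with the same treatment and baseline terms predicting the outcome.
- **Control-based.** Only Step 2 changes: probabilities come from placebo patients, "with adjustment of missing observation duration".
- **Tipping point.** This "will use the similar approach as PMM-MI with tipping values for the odds". Its Step 1 repeats the same baseline-only model.

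On-study events enter only through the observed part of the sum and the rule that flags the withdrawal segment as observed or missing. For sample size, SAP 1.3 assumes that the exacerbation count "follows a negative binomial distribution with a dispersion parameter of 1".

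**The concern.** A negative binomial count with dispersion 1 means that patients differ widely in underlying rate, so events already seen predict events to come. The imputation gives the same future rate to any two patients in the same arm with matching baseline covariates, whatever happened to them on study, and makes their imputed segments uncorrelated. This has two consequences.

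1. Completed counts vary too little between patients. The refitted dispersion is too low, and the imputed time is treated as more informative than it is.
2. If patients who exacerbate are likelier to withdraw, those with high rates are imputed at their arm's average rate. That arm's rate is then understated and the rate ratio moves.

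The sensitivity analyses exist to show that the primary result survives missing data. As written, PMM-MI reports better precision as more data are lost, and it needs a stronger assumption than the analysis it is meant to test: that withdrawal is unrelated to on-study events, given baseline. Because the tipping search ends when p exceeds 0.05, an understated standard error also pushes the tipping point outward.

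**Working it through.** **Inputs (SAP 1.3):** 462 per arm; rates 1.5 and 1.125 per year (ratio 0.75); dispersion k = 1; 0.95 year mean follow-up, that is, 5% missing time. For alpha, SAP 2.4.4.3 states "The overall Type-I error rate will be controlled at the two-sided 0.05 level".

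**Step 1: reproduce the stated power.**
Var(log RR) = [1/(1.5×0.95) + 1 + 1/(1.125×0.95) + 1]/462 = (0.702 + 1 + 0.936 + 1)/462 = 0.00787, so SE = 0.0887.
ln 0.75 = -0.2877; 0.2877/0.0887 = 3.24; 3.24 - 1.96 = 1.28, giving power 0.900. At alpha 0.049 it is 0.899. This agrees with SAP 1.3, where "the final alpha may be reduced to 0.049, which maintains approximately 90% power".

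**Step 2: how predictive on-study events are.** With k = 1, a placebo patient with y events in 0.5 year has expected further rate (1 + y)/(1/1.5 + 0.5) per year.
- y = 0: 1/1.167 = 0.86
- y = 3: 4/1.167 = 3.43

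Appendix K imputes both at the same rate.

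**Step 3: simulation A.** 3,000 trials per scenario; 26 segments, at most one event each; gamma frailty; treatment-only segment logistic models; 40 imputations; Rubin's formula. Random withdrawal:

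| Dispersion, missing time | PMM-MI SE | Primary SE | Complete-data SE | PMM-MI/primary |
|---|---|---|---|---|
| 1, 5% | 0.0851 | 0.0878 | 0.0862 | 0.969 |
| 1, 10% | 0.0843 | 0.0894 | 0.0862 | 0.943 |
| 0.5, 5% | 0.0729 | 0.0743 | 0.0728 | 0.981 |

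At k = 1 and 5% missing, the two estimates vary equally (empirical SD 0.0865 PMM-MI, 0.0866 primary), so the smaller standard error is not real precision. Coverage was 94.7% against 95.1%. At 10% missing, the PMM-MI empirical SD was 0.0892 and coverage 93.4%.

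**Step 4: event-driven withdrawal in simulation A.** Assumption: the withdrawal hazard is six times higher once a patient has two or more events. k = 1, 5% missing per arm.

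| Withdrawal | Bias in log RR against full data | PMM-MI RR |
|---|---|---|
| Random | +0.001 | |
| Event-driven, both arms | +0.005 | |
| Event-driven, dupilumab only | -0.018 | 0.736 |
| Event-driven, placebo only | +0.024 | 0.767 |

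The full-data RR is 0.750, and the Monte Carlo error of each bias is 0.0003 to 0.0005. At k = 0.5 the one-arm biases are -0.010 and +0.013. Dupilumab-driven at 10% missing, k = 1: -0.037, coverage 90.9%.

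**Step 5: the other two analyses (k = 1, 5% missing).**
- Control-based: RR 0.762 random, 0.750 dupilumab-driven (no penalty left), 0.778 placebo-driven. Its random-withdrawal SE of 0.0848 exceeds its empirical SD of 0.0811.
- Tipping point, dupilumab odds doubled, dupilumab-driven: RR 0.769, past the full-data value, but SE 0.0850 against empirical SD 0.0869.

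**Step 6: simulation B, a separate program.** 500 trials per scenario, gamma-Poisson events, and Appendix K's withdrawal-segment rule and 52-week offset. With k = 1, 5% missing and random withdrawal, the SE ratio to the primary was 0.968 to 0.969 under three withdrawal timings. The mean refitted dispersion fell from 1.00 to between 0.89 and 0.93. The SE was 2.1% lower at k = 0.5, 4.4% lower at k = 2, and 6.0% lower at 10% missing.

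With an assumed withdrawal chance after each event, PMM-MI gave RR 0.760 (7.5%, both arms), 0.790 (7.5%, placebo only) and 0.711 (10%, dupilumab only); the primary stayed at 0.750. Imputation conditional on the patient's count gave an SE ratio of 1.000 under random withdrawal, and RR 0.749 to 0.750 in every event-driven scenario at about 5% missing in the more affected arm.

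**The case against.** The strongest objections concern size.

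- **At 5% missing, the interval is close to nominal.** Against its own empirical SD, the PMM-MI standard error is only 1.6% low (0.0851 against 0.0865), with Monte Carlo error about 1.3% on that SD. In simulation B it was above the empirical SD (0.0866 against 0.0842). This stands as a statement about coverage. It does not remove the 3%: in both simulations PMM-MI reports 3% less error than the primary for an estimate that varies just as much, and at k = 1 it falls below the complete-data standard error.
- **The interval hardly changes.** The half-width shifts by 1.96×(0.0878 - 0.0851) = 0.005 on the log scale, whereas doubling the dupilumab odds moves log RR by ln(0.769/0.736) = 0.044. This stands at 5% missing.
- **The bias needs withdrawal that differs by arm.** When both arms withdraw by the same event-driven rule, the shift is small and toward the null. The withdrawal rules are assumptions, not figures from the documents. This stands. The plan's own summaries of withdrawal timing and reasons by arm would help show such a pattern, and the tipping shift can cover the location bias, but neither repairs the standard error.
- **Dispersion 1 may overstate what remains after covariates.** The imputation model includes prior-year exacerbations. At 0.5 the deficit is about 2% against the primary and nil against complete data. This stands as a range.
- **A corrected PMM-MI nearly reproduces the primary.** True, but the control-based and tipping-point analyses start from the same machinery and need a valid base.

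**Conclusion.** The concern holds. Appendix K's segment model omits on-study exacerbations, which conflicts with the negative binomial model used for planning and for the primary analysis, and nothing elsewhere in the SAP repairs it.

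Under random withdrawal at 5% missing time, the PMM-MI standard error is about 3% below the primary's at residual dispersion 1 (2% at 0.5, 4% at 2). At 10% missing and dispersion 1 it is about 6% below. The rate ratio is essentially unbiased if withdrawal is random or depends only on modelled baseline covariates. It moves toward benefit if dupilumab patients drive event-related withdrawal and toward the null if placebo patients do. At about 5% missing, the one-arm results ranged from 0.711 to 0.790 around 0.750, depending on the assumed rule.

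The tipping-point analysis keeps the understated standard error. The control-based standard error was not understated; that analysis loses its conservative margin only when dupilumab withdrawal is strongly event-driven.

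These sizes assume no baseline covariates other than treatment, with dispersion read as what remains after covariates. The 5% is the planning figure; actual loss may be smaller because off-treatment events are counted. The primary test is untouched. This should be corrected in the sensitivity analyses.

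**What to change.** In Appendix K, replace the segment-wise imputation with one from the negative binomial model, conditional on each patient's observed count and time. In each imputation, draw the gamma frailty given both, then draw the remaining events. For the missing period, use the own-arm rate for PMM-MI, the placebo rate for the control-based analysis, and a multiplied rate for the tipping point. In simulation A at 5% missing and dispersion 1, the own-arm version gave SE 0.0876 to 0.0879 (ratio to empirical SD 1.01) and RR 0.749 to 0.752 in all four withdrawal scenarios.

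The minimum change is one pooled segment model with the patient's shrunken on-study event rate as a covariate, updated after each imputed segment (RR 0.749, SE 0.0878 to 0.0882). Freezing that rate at withdrawal removes the bias but leaves the SE lower (0.0864 to 0.0869).

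The text of SAP 2.4.4.1 should be aligned. The cost is rewriting and reprogramming the imputation steps, and slightly wider intervals in the sensitivity analyses. No extra data are needed, and the primary analysis does not change.

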would occur during the missing observation period. A sequence of increasing/decreasing ratio will be used to generate different imputed datasets.

For each of the above methods, a negative binomial model will be fitted using each of the complete datasets composed of observed and imputed data, including the total number of observed and imputed events during the 52 weeks as the response variable, with the treatment group, region (pooled country), ICS dose at baseline (high dose ICS [yes/no]), smoking status at screening (current smokers or not), baseline disease severity (as % predicted post-bronchodilator FEV₁), and number of moderate or severe COPD exacerbation events within one year prior to the study (≤ 2 , 3, or ≥ 4) as covariates. Log transformed observation duration will be the offset variable for patients who complete the 52-Week treatment/study period, and log transformed 52 weeks will be the offset variable for patients who discontinue the study before Visit 16 (Week 52). SAS MIANALYZE procedure will be used to generate statistical inferences by combining results from the analysis with each dataset using Rubin's formula.

More details of the imputation and analyses methods are provided in Appendix K:

Subgroup analyses

To assess the consistency in treatment effects across different subgroup levels, subgroup analyses will be conducted for the primary efficacy endpoint with respect to:

- Age group (<65, ≥ 65 years; 40-64, 65-74, 75-85)
- Gender (Male, Female)
- Region
- Territory
- Race (White, Non-white)
- Ethnicity (Hispanic or Latino, Not Hispanic or Latino)
- Baseline weight (<70, ≥ 70 - <90, ≥ 90 kg; <60, ≥ 60 kg)
- Baseline BMI (<25, ≥ 25 - <30, ≥ 30 kg/m²)
- ICS high dose level at baseline (High-dose ICS, Non-high-dose ICS, No ICS)
- ICS dose level at baseline (< median, \geq median)
- Smoking status at screening (current smokers, former smokers)
- Number of moderate-or-severe COPD exacerbation events within one year prior to V1 (≤ 2 , 3, or ≥ 4)
- Number of severe COPD exacerbation events within one year prior to V1 (0, 1, ≥ 2 ; 0, ≥ 1)
- Baseline predicted post-bronchodilator FEV₁% (<50%, $\geq 50\%$)
- Baseline pre-bronchodilator FEV₁ (< median, \geq median)
- Baseline FEV₁ reversibility (<12%, $\geq 12\%$; < median, \geq median)
- Baseline fractional exhaled nitric oxide (FeNO) (<20, ≥ 20 ppb)
- Baseline eotaxin-3 (< median, \geq median)
- Baseline IgE (<100, ≥ 100 IU/ml)

- Baseline PARC (< median, \geq median)

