For each patient who early withdraws from the study, 40 sets of complete event count data can be obtained by summing the observed event count prior to withdrawal and each series of imputed binary events after withdrawal up to Week 52.

Step 4. A negative binomial model with the same set of covariates as in the primary analysis will be fitted to the 40 sets of complete datasets obtained in Step 3, so as to obtain 40 sets of treatment effect estimates and p-values accordingly. Log transformed observation duration will be the offset variable for patients who complete the 52-Week treatment/study period, and log transformed 52 weeks will be the offset variable for patients who discontinue the study before Visit 16 (Week 52). Then, the SAS MIANALYZE procedure will be used to generate statistical inferences by combining results from the 40 analyses using Rubin's formula.

Step 2, 3 and 4 will be repeated iteratively until the p-value for combined treatment effect of dupilumab compared to placebo estimated in Step 4 is >0.05 or the maximum applicable treatment effect has been reached.

Change from baseline in pre-BD FEV₁ at Week 12

- ***Pattern mixture model-multiple imputation (PMM-MI)***

Step 1. Monotone missing pattern was induced by Markov Chain Monte Carlo (MCMC) method using PROC MI: for patients who have missing values at intermediate visits, but have value at subsequent visits, the intermediate missing values were imputed assuming a multivariate normal distribution over observations from all visits. 40 datasets with a monotone missing pattern will be obtained using this method.

Step 2. For each of the imputed dataset with monotone missing pattern obtained in Step 1, the remaining missing data will be imputed using the regression method for the monotone pattern with adjustment for covariates including treatment groups, age, sex, height, region (pooled country), ICS dose at baseline (high dose ICS [yes/no]), smoking status at screening (current smokers or not), and baseline pre-BD FEV₁. All available data in the monotone missing pattern data will be used. 40 fully imputed datasets are obtained.

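### SAP Appendix K and section 2.4.4.1 put the primary-endpoint tipping shift on different scales; read as a subtraction, the Appendix K rule is valid only up to the smallest drawn placebo odds

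*SAP*

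**What the plan says.** SAP 2.4.4.1 raises the predicted odds for dupilumab patients with missing follow-up; "if the patient is on Placebo, the predicted odds value will be decreased". It then gives the scale: "A sequence of increasing/decreasing ratio will be used to generate different imputed datasets". It names no factors and refers to Appendix K for more detail.

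Appendix K, Tipping point analysis, Step 2, defines the odds per two-week segment as "the probability of having an event in the segment over the probability of being event-free in the segment". For placebo patients who need imputation, "the estimated odds for binary event will be deflated by decreasing a positive amount". For dupilumab patients, "the estimated odds for binary event will be inflated by increasing a positive amount". Step 3 draws each missing segment from a Bernoulli distribution with the resulting probability. The steps repeat until the combined p-value exceeds 0.05 "or the maximum applicable treatment effect has been reached". No size of amount, set of values, lower bound or definition of that maximum is given.

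The sentence that opens this part of Appendix K reads: "The tipping point analysis for severe exacerbation events will use the similar approach as PMM-MI with tipping values for the odds". It stands under a heading for moderate or severe events.

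**The concern.** A ratio and an amount are different rules and give different imputed data. A programmer will work from Appendix K, because that is where the steps are. There the phrase for the size of the shift is the same one used later in the appendix for pre-bronchodilator FEV1, where the shift is plainly added or subtracted.

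Subtraction suits FEV1. Odds cannot go below zero, and two-week odds in this trial are small to begin with. A common amount reaches zero first in the lowest-risk patients and then gives negative probabilities. On the dupilumab side a common addition is always valid, but it multiplies the odds of low-risk patients much more than those of high-risk patients.

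This analysis tests the primary result against missing follow-up, for which the main model imputes nothing. If the scale is unsettled, the choice of rule, and any truncation at zero, may be made after results are known.

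**Working it through.** **Inputs.** From SAP 1.3: placebo rate 1.5 per year, dupilumab rate 1.125, dispersion 1, mean follow-up 0.95 year, 462 patients per arm, two-sided alpha 0.05. From Appendix K: 26 two-week segments, odds = p/(1 − p). The documents give no two-week odds and no between-patient spread. The spread below is an assumption.

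**The plan's own figure.** SE of the log rate ratio = √{[1/(0.95 × 1.5) + 1/(0.95 × 1.125) + 2 × 1]/462} = 0.0887. |ln 0.75|/0.0887 = 3.24, and Φ(3.24 − 1.96) = 0.900. The stated 90% power reproduces, so the planning rate is a sound base.

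**Average placebo odds per segment.** Mean events m = 1.5/26 = 0.0577.

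| Conversion | p | Odds |
|---|---|---|
| p = m | 0.0577 | 0.061 |
| p = 1 − exp(−m) | 0.0561 | 0.059 |
| p = 1 − 1/(1 + m) | 0.0545 | 0.058 |

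The average is about 0.06. The middle row (0.0594) is used below.

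**Subtraction at the average.** Amounts of 0.01, 0.03 and 0.05 leave odds of 0.049, 0.029 and 0.009. Amounts of 0.06 and 0.10 give −0.001 and −0.041, which correspond to no probability.

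**Subtraction with patient spread.** Take lognormal odds with mean 0.0594 and log-scale SD s. The 1st percentile is 0.0594 × exp(−s²/2 − 2.326s). The share below an amount c is Φ{[ln(c/0.0594) + s²/2]/s}.

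| Assumed s | 1st percentile | Negative at c = 0.02 | at 0.03 | at 0.06 |
|---|---|---|---|---|
| 0.3 | 0.028 | 0.0% | 1.7% | 57% |
| 0.5 | 0.016 | 2.7% | 13% | 61% |
| 0.7 | 0.009 | 11% | 27% | 64% |

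So the average placebo odds can fall by only about 48%, 28% or 15% (1st percentile divided by 0.0594) before 1% of draws are invalid. Appendix K fits a separate logistic model in each segment and draws the coefficients 40 times. With about 462 × (1.5 + 1.125)/26 = 47 events per segment and nine coefficients, estimation noise adds further spread, which this table leaves out.

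**Addition on the dupilumab side.** Adding 0.06 multiplies the odds 4.1-fold for a patient at 0.5 events per year (odds 0.0194) and 1.5-fold at 3 per year (odds 0.1223).

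**Ratio, as in 2.4.4.1.** Factors of 0.8, 0.5, 0.2 and 0.1 applied to 0.0594 give 0.0475, 0.0297, 0.0119 and 0.0059. Any positive factor keeps the odds positive and the probability between 0 and 1 for every patient.

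**What the placebo side can move.** Take 5% missing follow-up, no placebo events in it, and dupilumab continuing at its own rate. The placebo rate becomes 1.5 × 0.95 = 1.425, and the planned rate ratio moves from 0.75 to 1.125/1.425 = 0.789. With the same SE, z falls from 3.24 to 2.66. The shift is |ln 0.95|/0.0887 = 0.58, so an observed z of 2.5 would fall to 1.92, below 1.96.

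**The case against.** The strongest reply is that the two passages can be read together. Section 2.4.4.1 fixes the scale as a ratio, and the amount in Appendix K may be whatever change that ratio produces in each patient. Appendix K does not use the word subtract for the odds, whereas it does for FEV1, and it does not say that one amount applies to everyone. On that reading no odds become negative. This is a possible reading, but the text does not compel it, and the shared phrase with the FEV1 shift points the other way. The passage still needs to be settled.

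A reader might go further and infer that the placebo side cannot be run at all. The documents do not support that. No amount is specified, amounts below the smallest drawn odds are valid, and the undefined maximum in the stopping rule could act as a bound. Nor do they prescribe a two-way grid here: combinations of shift parameters are described for FEV1 in SAP 2.4.4.2.1, while the exacerbation text speaks of a sequence.

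It is also fair that the stakes are modest at the planned effect, since even zero placebo events in the missing 5% would leave the result significant. That defence fails for a result near the threshold. The reference to severe events alone is a slip, because the governing heading and 2.4.4.1 both name moderate or severe events.

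**Conclusion.** The point holds as an inconsistency with a practical consequence. The SAP gives two scales for one analysis, and the scale in the operative appendix, read as a subtraction, is undefined once the amount exceeds the smallest drawn placebo odds. The average of about 0.06 follows from the planning rate. The 1st percentile of about 0.01 to 0.03 rests on assumed SDs of 0.7 to 0.3 and is not a figure from the documents. The placebo side is restricted and ill-defined beyond that limit. Only this sensitivity analysis is affected, and it matters most if the observed z lies near 2 to 2.5. It should be corrected before any unblinded analysis.

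**What to change.** In Appendix K, Step 2, replace the amount by the ratio of 2.4.4.1. Multiply the odds of dupilumab patients who need imputation by pre-set factors of at least 1, and those of placebo patients by pre-set factors between 0 and 1. Then convert back with p = odds/(1 + odds). State the range of factors in the SAP; its end points can also serve as the limit that the stopping rule leaves undefined. In the introductory sentence, change severe to moderate or severe. The cost is a few sentences in the SAP and about one line of code, with no change to data collection, the primary model, alpha or sample size.
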